1.3 SCHEDULE OF ACTIVITIES AND SAMPLE COLLECTION SCHEDULE

Table 1 Schedule of Activities

| Day | Protocol Reference | Day 1 ^a | | Day 2 | Day 3 | Day 4 | Day 5 | Day 6 | Day 10 | Day 15 | Day 29/ET |
|---|-----------------------|------------------------|------------------|----------------|--------------------|----------------|-------|----------------|----------------|--------------------|-------------------|
| Visits | | Screening (Predose) | V1 (Postdose) | V2 | Op V1 ^b | V3 | | V4 | V5 | Op V2 ^b | V6 |
| Visits window (days) | | 0 (–1) | –1 | | | +1 | | –1, +1 | –2, +2 | –3, +3 | ± 3 |
| Visit | | x | | x ^c | x ^c | x ^c | | x ^c | x ^c | x ^c | x ^{c, d} |
| Informed consent | 8 | x | | | | | | | | | |
| Local influenza test | 8.10.1 | x | | | | | | | | | |
| Local SARS-Cov-2 test ^e | 8.10.1 | x | | | | | | | | | |
| Inclusion/exclusion criteria | 5.1 5.2 | x | | | | | | | | | |
| Demographics | 8 | x | | | | | | | | | |
| Medical history | 8 | x | | | | | | | | | |
| Influenza vaccination history | 8 | x | | | | | | | | | |
| Randomization | 4.1 | x | | | | | | | | | |
| Baloxavir marboxil administration | 6.1.1 | x | | | | | | | | | |
| Oseltamivir BID administration ^f | 6.1.2 | x | | x | x | x | x | | | | |
| Palatability assessment | 8.11 Appendix 6 | | x ^g | | | | | | | | |

Table 1 Schedule of Activities (cont.)

| Day | | Protocol Reference | Day 1 ^a | | Day 2 | Day 3 | Day 4 | Day 5 | Day 6 | Day 10 | Day 15 | Day 29/ET |
|--|---|--------------------------|---------------------|--|------------------|--------------------|--------------------------|-------|----------------|----------------|--------------------|-------------------|
| Visits | | | Screening (Predose) | V1 (Postdose) | V2 | Op V1 ^b | V3 | | V4 | V5 | Op V2 ^b | V6 |
| Visits window (days) | | | 0 (–1) | –1 | | | +1 | | –1, +1 | –2, +2 | –3, +3 | ±3 |
| Visit | | | x | | x ^c | x ^c | x ^c | | x ^c | x ^c | x ^c | x ^{c, d} |
| Participant diary | Body temperature ^h | 4.1 8.2.2 | | x ⁱ (4 × daily) | | | x (2 × daily till Day 9) | | | x (once daily) | | |
| | CARIFS symptoms assessment ^j | 4.1 8.1.1.1 A5–1.1 | | x ⁱ (twice a day till Day 9) | | | | | | x (once daily) | | |
| Physical examination ^k | | 8.2.1 | x | | x | (x) | x | | x | x | (x ^l) | x |
| Vital signs | | 8.2.2 | x | | x | (x) | x | | x | x | (x ^l) | x ^m |
| Concomitant therapies assessment | | 6.8 | x | | x | (x) | x | | x | x | (x ^l) | x |

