4. STUDY DESIGN

4.1 OVERALL DESIGN

This is a multicenter, randomized, open-label, active-controlled (i.e., oseltamivir) study to assess the safety, pharmacokinetics, and efficacy of baloxavir marboxil compared with oseltamivir in Chinese pediatric participants aged 1 to <12 years with influenza symptoms within 48 hours of symptom onset.

Approximately 100 pediatric participants are planned to be enrolled. Of the overall sample size, approximately 1/3 participants who are 1 to <5 years old and 2/3 participants who are 5 to <12 years old are planned to be enrolled.

Participants will be screened and randomized on Day 1 and assigned in a 2:1 ratio to receive a single oral dose of baloxavir marboxil based on body weight (2 mg/kg for participants weighing <20 kg or 40 mg for participants weighing ≥20 kg to <80 kg or 80 mg for those weighing ≥80 kg))/XXXXXXXXXX for oral suspension or oseltamivir (twice a

day dose based on body weight) for 5 days. Re-screening of participants who fail to meet the inclusion and exclusion criteria will not be permitted for the same illness episode, as the time from symptom onset to the treatment window is limited to 48 hours. Either drug will be started at the time of randomization.

The total study duration for each participant will be 29 days, consisting of a 5-day treatment period (mandatory visits on Days 1, 2, and 4) and a 24-day follow-up period (mandatory visits on Days 6, 10, and 29). For the following assessments at clinic visits: physical examinations, vital signs, adverse events, concomitant therapies, clinical laboratory tests, and nasal/throat swabs. Visits on Day 29 or early termination visits can be conducted remotely. Throughout the treatment follow-up periods, the parents/caregivers will maintain a participant diary for each participant in order to record body temperatures (tympanic assessment), influenza symptoms, and acetaminophen use.

Temperatures will be recorded as follows.

- Days 1–3: 4 times daily (morning, noon, evening, and bedtime);
- Days 4–9: twice a day (morning and evening);
- Days 10–15: once daily.

Influenza symptoms will be recorded as follows.

- Days 1–9: twice a day (morning and evening)
- Days 10–15: once a day.

A study schema is provided in Section 1.2 (see Figure 1). A schedule of activities and a sample collection schedule are provided in Section 1.3 (see Table 1 and Table 2).

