#### 4.1.1 Visit Windows

**Table 5 Acceptable Time Windows for Parameters Other Than Data from the Patient Diary**

Time Point	Acceptable Time Window
(Scheduled Time Point)	
Pre-dose at Visit 1 (Day 1)	Before dosing on Day 1
Post-dose at Visit 1 (Day 1)	Between 0.5 and 4 hours after dosing (on Day 1)
Visit 2 (Day 2)	Day 2
Optional Visit 1 (Day 3)	Day 3
Visit 3 (Day 4)	Day 4
Visit 4 (Day 6)	Between Day 5 and Day 7 as follows: 

• if patient presents on Day 5 with no Day 4, and no Day 6 this will be classed as Visit 4.

• if patient presents on Day 5 with no Day 4, and Day 6 this will be classed as Visit 3.

• if patient presents on Day 5 with Day 4 and no Day 6 this will be classed as Visit 4.

Visit 5 (Day 10)	Between Day 8 and Day 12
Optional Visit2 (Day 15)	Between Day 13 and Day 22
Visit 6 (Day 29)	On or after Day 23
Withdrawal	Date of withdrawal + 14 days

\* if time is missing for data collected on Visit 1 where, per the schedule of activities, this data should be collected at 'v1 screening' or 'v1 post-dose' it is defined as 'Pre-dose at Visit 1 (Day 1)' or 'Post-dose at Visit 1 (Day 1)' respectively.

Measurements collected within the acceptable time window for each scheduled assessment time point, including data obtained at the time of withdrawal, will be used for the analyses of all endpoints at each assessment time point. For all patients with multiple values within a visit window, the value obtained closest to the target time point will be used. If two measurements collected with the same time deviation exist before and after the target time point, the measurement obtained before the target time point will be adopted for analysis. The assessment time point having no measurements within the corresponding acceptable time window will be considered as missing.

For summaries of data not collected by visit, such as adverse events, medical history and concomitant medications, all data up to the study completion/discontinuation date will be included.

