### **4.5.3 Pharmacokinetic Analyses**

Individual and mean plasma RO7191686 concentration versus time data will be tabulated and plotted. Individual plasma concentration at 24 and 72 hours postdose ( $C_{24}$  and  $C_{72}$ , respectively) of RO7191686 will be listed and summarized (mean, standard deviation, coefficient of variation, median, minimum, and maximum), and presented by age and/or bodyweight group.

As this study uses an optimized sparse PK regimen, individual PK parameters of RO7191686 (such as AUC,  $C_{max}$ ,) will be determined using a population PK analysis, and reported separately (modeling report).

Additional PK analyses may be conducted as appropriate.

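### SAP Table 5 drops the protocol's extra day for Visit 3 when Visit 4 falls on Day 7, so a compliant child seen on Days 5 and 7 loses Visit 3

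*SAP*

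**What the plan says.** **Protocol.** Section 4.1 requires "mandatory visits on Days 1, 2, and 4" and "mandatory visits on Days 6, 10, and 29". The visit-window row of Table 1 (Section 1.3) gives Visit 3 (Day 4) a window of +1 day and Visit 4 (Day 6) a window of −1 to +1 day. Central virology swabs and vital signs are scheduled at both visits.

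**SAP.** Table 5 in Section 4.1.1 covers everything except diary data. Its Visit 3 row reads "Visit 3 (Day 4) Day 4", with no extra day. The Visit 4 row reads "Between Day 5 and Day 7 as follows" and adds three rules for a Day 5 attendance:

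- no Day 4 and no Day 6: "if patient presents on Day 5 with no Day 4, and no Day 6 this will be classed as Visit 4";
- no Day 4 but a Day 6 visit: Day 5 becomes Visit 3;
- a Day 4 visit but no Day 6: Day 5 becomes Visit 4.

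The text under the table keeps one value per window, the one nearest the target. If two values lie equally far on either side, "the measurement obtained before the target time point will be adopted for analysis". A window with no value is treated as missing.

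**The concern.** The second Day 5 rule shows that the SAP means to honour the protocol's extra day for Visit 3, but it does so only if the next visit is on Day 6. No rule asks whether the child came on Day 7, which the protocol allows equally. In that case two in-window visits compete for one slot and the other slot stays empty.

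The SAP reports change in virus titer, change in virus RNA and the proportion positive by titer and by RT-PCR at each scheduled day, including Days 4 and 6 (Sections 4.3.2.3 to 4.3.2.6). It also summarises vital signs by visit, and change in vital signs is a component of the primary safety endpoint. An affected child would be absent from the Day 4 summaries. A sample taken on Day 5, when viral load would usually be higher than on Day 7, could stand as the Day 6 result. SAP Section 1 says that the planned analyses have not changed from the protocol, so this does not look like a deliberate departure.

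**Working it through.** The plan states no figure on this point, so there is none to reproduce. The check applies the Table 5 rules to every attendance pattern that the protocol allows.

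**Inputs**

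- Visit 3 permitted on Days 4–5, Visit 4 on Days 5–7 (Protocol Table 1).
- Day 5 rules, nearest-value rule, tie rule and missing rule (SAP Section 4.1.1).
- 67 children planned on baloxavir marboxil and 33 on oseltamivir (SAP Section 2.2).

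**Step 1: compliant pairs.** Two possible days for Visit 3 times three for Visit 4 gives 6. Removing the pair with both visits on Day 5 leaves 5.

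**Step 2: apply Table 5, in whole study days.**

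| Attended (Visit 3, Visit 4) | Table 5 Visit 3 | Table 5 Visit 4 | Unused |
|---|---|---|---|
| 4, 5 | Day 4 | Day 5 | none |
| 4, 6 | Day 4 | Day 6 | none |
| 4, 7 | Day 4 | Day 7 | none |
| 5, 6 | Day 5 | Day 6 | none |
| 5, 7 | missing | Day 5 | Day 7 |

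Four of five are classified as the protocol intends; one is not.

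**Step 3: the failing pair.** There is no Day 4 and no Day 6 visit, so Day 5 becomes Visit 4. Day 7 is also in the Visit 4 window. The distances from Day 6 are |5 − 6| = 1 and |7 − 6| = 1, a tie, so the earlier value is kept. The SAP does not say whether distance is counted in days or hours. By the clock, the nominal times are 96 h and 144 h against a target of 120 h, so both are 24 h away and the hour of each visit decides. If visit times vary symmetrically, either value is equally likely to be kept. Under both readings Visit 3 is missing and one sample is unused.

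**Step 4: what the child loses.** Swabs are due on Days 2, 4, 6 and 10. The child supplies 3 of these 4 timepoints to the by-visit summaries, although all 4 swabs were taken in window.

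**Step 5: size per child.** One child is 1/33 = 3.0% of the planned oseltamivir arm and 1/67 = 1.5% of the planned baloxavir arm. For a proportion positive with x of n positive:

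- Day 4: dropping a positive child lowers it by (n − x)/[n(n − 1)], and dropping a negative child raises it by x/[n(n − 1)]. Neither exceeds 1/n.
- Day 6: using a positive Day 5 result in place of a negative Day 7 result raises it by exactly 1/n.

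So one child moves a by-visit proportion by at most 3.0 percentage points on oseltamivir or 1.5 on baloxavir at the planned numbers. The virology denominators contain only infected children who were positive on Day 1, so the true share per child can be somewhat larger.

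**Step 6: test the repair.** If Day 5 is classed as Visit 3 when there is no Day 4 visit and a visit occurs on Day 6 or Day 7, all five pairs map as intended. Days 5 and 7 give Visit 3 = Day 5 and Visit 4 = Day 7, with nothing dropped. A child seen only on Day 5 still maps to Visit 4, as now.

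**The case against.** The best case for leaving Table 5 alone is that this is a narrow edge case in a descriptive study. Four of the five compliant pairs are handled correctly. Day 5 lies in the protocol's own Visit 4 window, so classing it as Visit 4 is reasonable when the child is not seen again by Day 7. No hypothesis is tested. All of that stands, and it limits the importance of the point; it does not make the result for Days 5 and 7 correct.

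A reader might also infer more than the documents support:

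- *That the Day 7 sample is always discarded and Day 5 always appears as Day 6.* This holds only if distance is counted in whole days.
- *That the shedding comparison as a whole is compromised.* Time to cessation of shedding is defined from the start of treatment and the virology AUC from assessment times. The SAP does not say that either is restricted to windowed values. The rule is the same in both arms, and no bias between arms has been shown.
- *That safety reporting is broadly affected.* Adverse events are summarised from all data regardless of windows. Safety laboratory tests are scheduled on Day 6 but not on Day 4, so Visit 3 has no scheduled laboratory value to lose.
- *That C24 and C72 will mix very different sampling times.* Table 5 is broad enough to include PK samples, and a sample taken at a Day 5 visit would be at about 4 × 24 = 96 h. But Protocol Table 2 schedules these samples by hours after dosing, Protocol Section 8.4 requires actual clock times, and SAP Section 4.5.3 refers to "Individual plasma concentration at 24 and 72 hours postdose". That the calendar-day windows override those definitions is inference. This supports a request for clarification and no more.

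**Conclusion.** The point holds as a small, definite error in a stated rule. SAP Table 5 does not carry over the protocol's extra day for Visit 3 when Visit 4 is on Day 7. For that pattern Visit 3 is set to missing, one in-window sample is left out of the by-visit summaries, and a Day 5 value can be reported as Day 6. The effect is confined to by-visit virology (change in titer and RNA, proportion positive) and the Day 4 and Day 6 vital signs.

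The conclusion that the rule misclassifies rests only on the text. The total effect cannot be given, because the documents do not say how often children will be seen on Days 5 and 7. What can be said is the size per child: about 3% of the planned oseltamivir arm and 1.5% of the baloxavir arm. That the Day 5 value is the one kept assumes counting in whole days. It is worth correcting because the correction is simple, not because the effect is known to be large.

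**What to change.** In SAP Table 5, replace the Day 5 rules with: a Day 5 attendance is Visit 3 when there is no Day 4 visit and a visit occurs on Day 6 or Day 7; otherwise it is Visit 4. This also settles attendance on Days 4, 5 and 6, for which Table 5 now has no rule: Day 5 would be a Visit 4 candidate and Day 6 would be kept as nearer the target. State as well whether distance from target is measured in study days or in hours.

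As a secondary clarification, add a sentence to SAP Section 4.5.3 that the C24 and C72 summaries use the recorded elapsed time after dosing rather than the Table 5 calendar-day windows, with limits to be set by the sponsor.

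The cost is SAP wording and the matching change to the visit derivation. Trial conduct and data collection do not change, since the visit dates and PK clock times are already recorded. Depending on the limits chosen, some PK values may move out of the C24 and C72 summaries.

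### SAP Table 5 does not consider Day 7 when classifying a Day 5 visit, so a child seen in window on Day 5 (Visit 3) and Day 7 (Visit 4) loses Visit 3 and one of two on-time values

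*SAP*

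**What the plan says.** The schedule of activities in Protocol Section 1.3 (Table 1) gives Visit 3, nominally Day 4, a window of +1 day. It gives Visit 4, nominally Day 6, a window of one day either side. Visit 3 may therefore fall on Day 4 or 5, and Visit 4 on Day 5, 6 or 7.

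SAP Section 4.1.1 (Table 5) sets the analysis windows for all data other than the diary. The Visit 3 row lists Day 4 alone. The Visit 4 row reads "Between Day 5 and Day 7 as follows" and adds three bullets on Day 5 attendances:

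- First bullet: "if patient presents on Day 5 with no Day 4, and no Day 6 this will be classed as Visit 4".
- Second bullet: "if patient presents on Day 5 with no Day 4, and Day 6 this will be classed as Visit 3".
- Third bullet: Day 5 with a Day 4 visit and no Day 6 visit is Visit 4.

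Three general rules follow the table. With several values in a window, "the value obtained closest to the target time point will be used". With equal deviation on either side of target, "the measurement obtained before the target time point will be adopted for analysis". For an empty window: "The assessment time point having no measurements within the corresponding acceptable time window will be considered as missing".

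SAP Section 1 states that the planned analyses have not changed from the protocol.

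**The concern.** The second bullet shows that the SAP means to honour the protocol's extra day for Visit 3: a child who comes on Day 5 and again on Day 6 keeps both visits. Day 7 is just as much in window for Visit 4, yet no bullet mentions it. A child who comes on Day 5 and Day 7 has complied fully, but falls under the first bullet and is treated as having missed Visit 3.

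Table 5 feeds the by-visit summaries. Vital signs and respiratory samples are scheduled at both Visit 3 and Visit 4, so each affected child would lose valid data from these summaries:

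- vital signs, whose change from baseline is one of the primary safety endpoints (SAP 4.2.2.4);
- change in virus titer and in virus RNA (SAP 4.3.2.3 and 4.3.2.4);
- the proportions positive by titer and by RT-PCR (SAP 4.3.2.5 and 4.3.2.6).

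The result would show a missing visit where none was missed, and an on-time measurement would go unused.

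**Working it through.** **Inputs.** Protocol Table 1: Visit 3 on Day 4 or 5; Visit 4 on Day 5, 6 or 7. SAP Table 5: Visit 3 is Day 4; Visit 4 is Days 5 to 7, subject to the three bullets; then closest to target, earlier value on a tie, empty window missing. I read the second bullet as Day 6 present, because reading it as Day 6 absent would contradict the first. The plan states no figure on this point to reproduce.

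**Enumeration.** Two possible days for Visit 3 times three for Visit 4 gives 6 pairs. Removing 5/5, where both visits would share a day, leaves 5. Deviations are counted in whole days, the unit of the table.

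| Visit 3 day / Visit 4 day | Bullet that applies | SAP Visit 3 | SAP Visit 4 | Not used |
|---|---|---|---|---|
| 4 / 5 | third | Day 4 | Day 5 | none |
| 4 / 6 | none needed | Day 4 | Day 6 | none |
| 4 / 7 | none needed | Day 4 | Day 7 | none |
| 5 / 6 | second | Day 5 | Day 6 | none |
| 5 / 7 | first | missing | Day 5 | Day 7 |

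**The failing pair, step by step.**

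1. There is no Day 4 and no Day 6 visit, so the first bullet makes Day 5 Visit 4.
2. Nothing is left in the Visit 3 window, so Visit 3 is missing.
3. Day 7 is also in the Visit 4 window. The deviations are |5 − 6| = 1 and |7 − 6| = 1, a tie.
4. The tie rule keeps the earlier value, Day 5. The Day 7 value is not used.

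**Sensitivity to the unit.** The SAP does not say whether deviation is counted in days or hours. Assume the Day 6 target is 120 h after dosing, since 24 × (6 − 1) = 120:

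- Samples at 96 h and 144 h deviate by 24 h and 24 h: tie, Day 5 kept.
- Samples at 99 h and 145 h deviate by 21 h and 25 h: Day 5 kept.
- Samples at 93 h and 141 h deviate by 27 h and 21 h: Day 7 kept.

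Counting in hours can change which value survives. It does not restore Visit 3, and one of the two values is still unused.

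**Which data are affected.** A value is lost only where a parameter is measured at both visits. In Protocol Table 1 that holds for vital signs and respiratory samples. Laboratory tests are scheduled at Day 6 but not at Day 4, so a Day 7 laboratory result with no Day 5 result would still be used for Visit 4. Adverse events are not windowed by visit (SAP 4.1.1).

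**Weight of one child.** With the planned arms of 33 and 67 (SAP 2.2), one child is 1/33 = 3.0% of the oseltamivir denominator and 1/67 = 1.5% of the baloxavir denominator. The virology denominators can be no larger, because those analyses use FASi children positive on Day 1.

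**The case against.** The strongest reply is that this is an edge case in a descriptive study, and that several larger claims a reader might draw from it fail. Most of that is right.

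- **That the SAP ignores the +1 window altogether.** The Visit 3 row taken alone suggests this, but the second bullet accepts Day 5 as Visit 3 when a Day 6 visit exists. The gap is Day 7 only.
- **That the frequency can be estimated from weekends.** If sites avoid Sundays, a child starting on Thursday has Day 4 on a Sunday and may be seen on Monday, Day 5. With even enrolment that is 1 in 7, about 14 of 100. But this child's Day 6 is a Tuesday, so nothing pushes Visit 4 to Day 7, and the 5/6 pair maps correctly. Day 4 and Day 6 are two days apart while Saturday and Sunday are adjacent, so weekend avoidance alone cannot force 5/7. Home visits by mobile nurses at appropriate sites (Protocol Section 8) weaken the premise further.
- **That Visit 4 data are shifted by 48 h.** Day 5 and Day 7 are each one day from Day 6, and both are in the protocol window. A Day 5 value is no less admissible for Visit 4 than a Day 7 value. The 48 h is the gap between the two candidate values, not an error against target.
- **That the Day 7 value is always the one lost.** This depends on the unstated unit, as shown in the working.
- **That classing a lone Day 5 visit as Visit 4 is an error.** Day 5 is in window for both visits and equally far from each target. Choosing Visit 4 is an acceptable prespecified convention.

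It can also be argued that the first bullet's absence of Day 6 was meant as absence of any Visit 4 attendance. The problem would then vanish. But the bullets are written in study days and do not say so, and a programmer would have to guess.

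What survives is the 5/7 pair itself: a stated rule that turns two compliant visits into one.

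**Conclusion.** The point holds in a narrow form. As written, SAP Table 5 mishandles one of the five in-window day pairs. For a child seen on Day 5 and Day 7 with no Day 4 or Day 6 visit, Visit 3 is recorded as missing and one of two on-time values is unused in the by-visit summaries of vital signs, virus titer, virus RNA and the proportions positive. This rests on reading the bullets literally, in study days. That the Day 5 value is the one kept rests further on counting deviation in whole days.

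The number of children affected cannot be derived from the documents and may be small or zero. No hypothesis test is at stake, since all analyses are descriptive. The text also does not settle whether time to cessation of shedding and AUC, which use assessment times, would drop the unused sample, so no effect on them is claimed. The correction is worth making before database lock because the rule departs from the protocol windows without saying so and is cheap to repair.

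**What to change.** In the Visit 4 row of SAP Table 5, change two bullets:

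- First bullet: a Day 5 visit with no Day 4 visit, and no visit on either Day 6 or Day 7, is Visit 4.
- Second bullet: a Day 5 visit with no Day 4 visit, and a visit on Day 6 or Day 7, is Visit 3. Visit 4 is then Day 6 if present, otherwise Day 7.

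Leave the third bullet and the tie rule as they are. The 5/7 pair then gives Visit 3 = Day 5 and Visit 4 = Day 7, with nothing missing or unused, and the tie no longer arises for this child. The other four pairs, the lone Day 5 visit, and attendance on Days 4, 5 and 7 are classified as before.

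The cost is one table cell and one line of programming. No new data are needed.
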